**Description of study instruments (those marked with † are included in the NINDS CDE)**

- Structured Clinical Interview for DSM-IV (SCID-IV): A structured diagnostic interview scheduled designed to measure the presence/absence of the full range of DSM-IV Axis I mental disorders. The SCID-IV is regarded as the "gold standard" for assessing mental disorders, having been used in over 100 published studies as of 1992.
- Clinician-Administered PTSD Scale for DSM-IV (CAPS): A structured clinical interview designed to assess the 17 symptoms of PTSD outlined in the DSM-IV. The CAPS allows the interviewer to make current (past month) and lifetime DSM-IV diagnoses of PTSD. The frequency and intensity of each symptom on the CAPS is rated on separate 5-point scales, yielding both dichotomous and continuous scores (range = 0 to 136) for each symptom and for the disorder as a whole. Test-retest reliability studies have consistently yielded coefficients ranging from .90 to .98, and internal consistency has ranged from .85 to .87 for symptom clusters to .94 for the entire scale. The 17-item CAPS has become the standard for psychopharmacologic outcome trials in PTSD.
- †PTSD Checklist-military version(PCL-M): A self-report inventory of the 17 DSM-IV symptoms that define the disorder PTSD. Symptoms are rated on 5-point Likert scales, yielding a score ranging from 17 to 85. The PCL-M has been shown to be a reliable and valid measure of military trauma-

related PTSD symptoms in a variety of special populations. The PCL-M is useful as a continuous measure of PTSD symptom distress in war-zone exposed Veterans. A score of 50 or greater has high diagnostic sensitivity (.81) and specificity (.83). Test-retest reliability (.96) and internal consistency ( $\alpha=.93$ ) for the PCL-M are exceptional.

- †Patient Health Questionnaire-9 (PHQ-9): The 9-item depression module of the Patient Health Questionnaire, a self-report version of the PRIME-MD used to diagnose major mental disorders. The PHQ-9 items correspond with DSM-IV criteria for depression, with each item scored from “not at all” to “nearly every day.” Items of the PHQ-9 are internally consistent ( $\alpha = 0.86-0.89$ ) and the questionnaire exhibits high test-retest reliability coefficients. Agreement between the PHQ-9 and clinician-based interview diagnosis of major depression is high, with a sensitivity of 88% and a specificity of 88% using a PHQ-9 score  $\geq 10$ .
- †Alcohol Use Disorders Identification Test-Consumption (AUDIT-C): A 3-item modification of the AUDIT questionnaire that inquires about frequency and quantity of typical alcohol consumption, and the frequency with which the respondents report an episode of heavy drinking in the past year (defined as 6 drinks per one occasion in men and 4 drinks per one occasion in women). The AUDIT-C demonstrates excellent sensitivity and specificity for detection of heavy drinking and is used as a standard screening tool for alcohol problems in VA primary care settings.
- †Brief Symptom Inventory (BSI): This shortened version of the SCL-90 is self-report measure with 18-items rated on a 5-point rating scale. The BSI includes 3 clinical scales: Depression, Anxiety and Somatization) and an overall Global Severity Index. This questionnaire takes approximately 10 minutes to complete
- †Rivermead Postconcussive Questionnaire (RPQ) - A 16-item self-report measure of presence and severity of the 16 most commonly reported postconcussive symptoms. Items are reported on a 0-4 scale ranging from "not experienced at all" to "severe".
- †Neurobehavioral Symptom Inventory (NSI). The NSI is a 22 item questionnaire designed to assess the presence and severity of common cognitive, emotional, sensory, and somatic symptoms that can occur after traumatic brain injury. Patients rate on a 5-point scale the extent to which each symptom has affected them (rated from “absent” to “very severe”). Anchor descriptions are provided for level of severity. It is widely used in VAs across the country for the TBI Second Level Evaluation.
- †Satisfaction with Life Scale (SWLS) - includes 5 items answered on a 7-point Likert scale ranging from 1=strongly disagree to 7=strongly agree. Total score ranges from 7-35 with higher scores indicating better satisfaction with life.
- †Craig Handicap and Assessment Reporting Technique (CHART-DF): provides an objective measure of the degree to which impairments and disabilities result in long-term handicaps.
- Montreal Cognitive Assessment (MoCA): A cognitive assessment instrument designed to detect cognitive impairment and provides a brief assessment of global cognitive function, including short-term memory recall, executive function, sustained attention, calculation, language, and orientation. Scores range from 0-30 with lower scores indicating greater impairment. Test-retest reliability is high with less than one point variation. Internal consistency is good (Cronbach  $\alpha=0.83$ ). To correct for education, 1 point is added for those with less than 12 years of education.
- Wechsler Test of Adult Reading (WTAR): A neuropsychological test designed to provide estimates of premorbid intellectual functioning. This estimate is derived from the ability to read a list of irregular words, as single word reading recognition ability has been shown to be resilient to the effects of TBI.
- †WAIS-III Letter-Number Sequencing Subtest. The examiner reads a combination of numbers and letters that the subject is then asked to reproduce orally with the numbers first in ascending order, followed by the letters in alphabetical order. As the test progresses, items presented to the subject contain more numbers and letters. This test requires concentration, attention, and an ability to store and organize information in memory for a short duration (5-10 min.)
- †Grooved Pegboard: This is a test of fine motor coordination and speed. In this test, subjects are required to place 25 small metal pegs into holes on a 3" x 3" metal board. First the dominant hand is tested, and subjects are asked to place the pegs in the holes as fast as they can. This is repeated with the nondominant hand, and the total time for each hand is recorded. This test has been shown to be sensitive to statin manipulations.

- Auditory Consonant Trigrams: This is an adaptation of the Brown-Peterson technique. The task assesses short-term retention and due to the different lengths of interference activity, performance can be assessed at several difficulty levels. Three letters are read to the participant followed by a number. The subject begins to subtract from the number by threes until zero, three, nine, or 18 seconds have passed at which time the examiner asks the participant to recall the three letters. The test discriminates controls from persons with cognitive impairment.
- Simple and Choice Reaction Time, Continuous Visual Memory Test, Digit Vigilance Test: These tests are part of a battery of computerized tests that was developed and validated in all adult age groups by the U.S. Department of the Navy to rapidly measure cognitive processing efficiency. In the simple reaction time task, symbols are presented on a computer screen and subjects are asked to strike a particular key on the keyboard as soon as a symbol appears. For the choice reaction time task, two different symbols appear at random on the screen and subjects are asked to respond to only one of the symbols. For the continuous performance test, numerous symbols appear on the screen and subjects are asked to respond to only one symbol when it is preceded by another particular symbol. For all subtests, this process is repeated ten times and the average of ten trials is used. Several studies have shown the battery to be sensitive to the effects of medications, including amphetamines and nicotine, and to mild head injury. It has good test-retest reliability and validity when compared to other well established tests.
- †Rey Auditory Verbal Learning Test (RAVLT): This is a brief verbal learning and memory instrument, consisting of a 15-item word list presented to the subject orally in five consecutive trials followed by a second list. The number of words recalled is recorded after each presentation of the list and the interference or second list. A delayed recall of the list is given followed by a yes/no recognition. It has excellent test-retest reliability (.51 - .70) and validity as demonstrated by a good correlation with other memory tests (.50 - .56).
- †Processing Speed Index from the WAIS-III: Based on 2 subtests of the WAIS-III: Digit Symbol and Symbol Search. For Digit Symbol, examinee must accurately fill in symbols according to matched number-symbol pairs in a key. For Symbol Search, examinee determines whether either of 2 target symbols match any of the symbols in a search group.
- †Digit Span of WAIS-III: A test of attention and memory from the WAIS-III.
- †Controlled Oral Word Association Test (COWAT): assesses the ability to quickly generate words beginning with certain letters. This test has been shown to be sensitive to the effects of frontal lobe dysfunction and to the effects of TBI: Total number of words generated will be used in this study.
- †Trail Making Test: A measure of scanning, divided attention, and cognitive flexibility (a type of executive functioning). Total score is based on time to complete the task, and individuals with mild TBI tend to be slower than healthy controls on this task.
- Test of Memory Malingering (TOMM): A widely used symptom validity test that will be used to detect poor effort, and thus invalid results, on neuropsychological tests. The TOMM is face valid and performance appears to be unaffected by mild cognitive or neurological impairment.

*Note: Three of the NINDS-CDE assessments: the Functional Independence Measure – Cognitive and Motor Subscales, and the Glasgow Outcome Scale – Extended, will not be utilized because of their inappropriateness for mTBI. The remainder of the Core NINDS-CDE assessments and selected supplemental measures will be utilized and are described above.*

#### **Data management:**

A master database will be set up using Microsoft SQL2000 server software at VA Puget Sound by the Data Manager. Data will be double-data entered weekly through a web based data center application. The web application and backend processes will aid in checking data integrity. The Data Manager will generate weekly reports of data discrepancies. The Study Coordinator will be responsible for rectifying data entry errors. Database maintenance includes weekly backup to tapes, which are stored at a safe location, and SQL server routine maintenance. SQL server security will include sign-on authentication and access to the database will be password protected. Laboratory data (e.g., CSF t-tau, p-tau181, and APOE genotype) will be generated at several different laboratories. These laboratories will enter data into their own databases and will export them as an Excel file (or similar easily readable file) to the Database Manager. All files sent to the Database Manager will be encrypted. These data will be linked via unique study identification numbers assigned to each study subject.

Confidentiality: All study information will be recorded on standardized case report forms (CRFs). CRFs

will be labeled only with the unique study identification number assigned to each study subject. Source documents will be kept separately from CRFs in locked filing cabinets in locked offices. Study records will be kept separate from the subject's medical record. Coded information from the CRFs will be entered into the study database. The database will reside in a restricted access folder on a VA server. Only personnel having the correct user name, password, and signing on from a computer with the appropriate IP address will have access. The link between study code and identifying information will be kept by the PI in a locked file or on a computer with password protection and will not be available to anyone other than members of the research team.

Only the investigators and the research staff will have access to the original research data. Appropriate regulatory agencies (Office for Human Research Protections [OHRP], Department of Veterans Affairs [DVA], local Institutional Review Boards [IRBs]) may view records that contain identifying information. Data will not be revealed to insurance companies or other individuals or organizations.

We plan to obtain a Federal Certificate of Confidentiality to protect subjects from compelled disclosure of sensitive information and genetic testing results. However, the Certificate will not prevent the research team from taking steps, including reporting to authorities, to prevent serious harm to the subject or others. We are not collecting any health information that is reportable to local health agencies.

Because a Records Retention Schedule approved by National Archives and Records Administration is required to destroy Federal records, and because at this time there is not such a schedule for VA research records, we must retain data pending approval of such a schedule. Therefore, all study data, including the link between subject identities and study code numbers will be maintained under secure conditions (locked cabinets and/or password-protected computers) until we have permission to destroy them or until data analysis is complete (whichever comes later). At that time, the link will be destroyed and all study data will become anonymous. Anonymous study data will be kept indefinitely.

**Sharing Study Results:** Results of diagnostic tests performed as part of the screening procedures (laboratory results) may be shared with study participants and/or their primary care providers if desired by the study participants. Individual results of the assessment instruments will not be shared, but if the participant wishes, a summary of the results will be provided to the participant and/or his/her mental health care provider after the participant has completed the study. A release of information form will be obtained before any results are shared with anyone but the participant. Results of CSF biomarkers and APOE genotype will not be shared.

### **Data Analysis:**

**Specific Aim 1:** To examine the effects of 12 months of treatment with simvastatin 40 mg/day on CSF concentrations of tau biomarkers (t-tau, p-tau181, and t-tau:p-tau181 ratio) and brain-derived neurotrophic factor (BDNF) in Iraq and Afghanistan Veterans with repetitive blast concussion mTBI.

**Hypothesis 1:** Compared to placebo, simvastatin will reduce levels of CSF t-tau, p-tau181, and p-tau181:t-tau ratio; and will increase level of CSF BDNF.

**Specific Aim 2:** To explore the effects of 12 months of treatment with simvastatin 40mg/day on CSF A $\beta$ 42, and biomarkers of oxidative stress and neuroinflammation in Iraq and Afghanistan Veterans with repetitive blast concussion mTBI.

**Hypothesis 2:** Compared to placebo, simvastatin will reduce levels of CSF A $\beta$ 42, and biomarkers of oxidative stress (F2-isoprostanes) and neuroinflammation (interleukin-6 [IL-6], IL-8, and S100 $\beta$ ).

**Sample Size, Effect Size, and Power** are based on the change from baseline in the CSF t-tau, p-tau181, and BDNF (Specific Aim 1). We will recruit 120 subjects for this study. Assuming a drop-out rate of about 17%, there will be approximately 50 subjects per treatment group (simvastatin vs. placebo). Using an overall Type I error rate of 5% and a Bonferroni adjustment based on four primary endpoints: CSF t-tau, p-tau181, p-tau181:t-tau ratio, and BDNF (i.e., setting  $\alpha = 0.05/4 = 0.0125$ ), 50 subjects per treatment group yields 80% power to detect an effect size (i.e., | Mean | / SD) of 68% and 90% power to detect an effect size of 77%. For the preliminary study of statin treatment described in Preliminary Findings, change from baseline in t-tau was -107 pg/ml (SD = 129 pg/ml), yielding an observed effect size of 83%.

We believe that this is a conservative estimate of statistical power, because: 1) the estimated t-tau changes are based on only 14 weeks of statin treatment (the duration of the preliminary study). We expect a larger difference in change from baseline between the two treatment groups with one year of treatment, as proposed in this study; and 2) in our pilot data the variability in p-tau181:t-tau ratio in the mTBI subjects was low and the age group is relatively young (21-50), which should reduce variation of CSF t-tau levels, since t-tau is correlated with age. Also, we will stratify during randomization by two factors that potentially influence t-tau

levels: gender and number of blast trauma exposures. The stratification should decrease the variability in the estimate of treatment effect and thus increase statistical power to detect a smaller change from baseline.

### **Statistical analysis.**

**Primary analysis plan:** All CSF biomarkers, neuropsychological test scores, behavioral assessments, and functional and quality of life measures are continuous variables. Gender, APOE genotype, and number of mTBIs ( $\geq 5$  or  $< 5$ ) are categorical. Analysis of covariance (ANCOVA) will be used to assess the change from the baseline in all biomarkers as well as neuropsychological test scores. All outcomes are continuous variables. The distribution of model residuals will be assessed and outcome variables may be transformed to conform to assumptions of the statistical tests (e.g., for non-normality). The response variables will be biomarker concentrations at the end of the study (12-month visit), and predictor variables will include biomarker concentrations at the beginning of the study (baseline visit), treatment arm assignment (simvastatin vs. placebo), as well as the variables that were used for stratification of treatment assignment (i.e., gender and number of blast exposures). To examine effects of statin treatment on memory and cognition, the response variables will be test scores at the end of the study (12-month visit). The predictor variables will include test scores at the beginning of the study (baseline visit), treatment arm assignment (simvastatin vs. placebo), as well as the variables that were used for stratification of treatment assignment (i.e., gender and number of blast exposures). Significance of treatment arm effect will be adjusted for multiple tests (i.e., the four primary endpoints) using the method of Holm (1979).

The primary analysis will include all subjects who were randomized and completed the study. A secondary analysis will use a linear mixed-effects model to include all subjects who were randomized and had a baseline visit, including subjects with just a baseline visit as well as subjects with a baseline visit and an early termination visit. Baseline differences, if any, between study completers and non-completers will be summarized.

**Secondary analysis plan:** In addition to the above primary analysis, secondary analyses will include the following:

- Correlation analyses to assess relationships among CSF biomarkers and how they change over time relative to each other.
- Exploring what other covariates (such as serum cholesterol levels) may be important in predicting changes from baseline in CSF AD biomarkers
- An assessment of the nature of missing observations (i.e., random vs. systematic).
- One-sample tests assessing change from baseline within each treatment group, using parametric and/or nonparametric tests.
- Fisher's exact test comparing the proportion of values of change from baseline that are less than zero between the two treatment groups, because *consistent* subtle declines associated with simvastatin treatment could be very meaningful in terms of elucidating prevention mechanisms.

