**Baseline:** The Baseline visit will be scheduled within 4 weeks of the Screening visit. The Baseline visit consists of 2 separate appointments within a week of each other. During the first visit, vital signs will be obtained, a brief physical examination will be performed, concurrent medications will be recorded, a blood draw will be performed for measurement of plasma lipids and inflammatory markers, and an LP will be performed as described in detail below.

During the second baseline visit, the neurocognitive test battery will be administered and behavioral assessments will be performed. Comorbid PTSD will be assessed with the CAPS. A detailed description of all study instruments is below.

**Randomization, titration, and continued study treatment:** Upon completion of all baseline procedures, participants will be randomized to receive simvastatin or placebo. Stratification factors will include age (<40 vs ≥ 40 years), gender, and number of blast trauma exposures (<5 and ≥5). Permuted block randomization will be used within each stratum. Varying the block size reduces the predictability of treatment assignment. Separate blocked sequences will be generated for each of the three strata and provided directly to the Research Pharmacist at the VA Puget Sound, who will prepare study drug for dispensing.

Simvastatin will be started at 20 mg qhs and titrated over 2 weeks to a final dose of 40 mg qhs. Placebo will be titrated at week 2 correspondingly. We assume a drop-out rate of ten percent, yielding a total sample size of 50 subjects per group at the end of the study.

**Safety and compliance visits:** Four additional visits will be scheduled at 6 weeks and at 3-, 6-, and 9-months of treatment to monitor adverse effects, assess compliance with study medications, and dispense study medication. Each visit will include measurement of vital signs, update of concurrent medications, and any self-report of adverse effects. Pill counts will be used to assess compliance. Safety assessments as described below will be performed.

**Outcome assessment:** Outcome assessments will be obtained in two visits at the end of 12 months of treatment. Procedures for outcome assessments duplicate the procedures performed during the Baseline visits as described above. Pill counts will be used to assess compliance with medication use.

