#### **(6) Inclusion of Women and Minorities:**

Because of the requirement that blast trauma group participants have experienced at least one blast trauma exposure, the majority of participants in this group will come from MOSs with high blast trauma exposure: Infantry, Combat Engineers, Explosive Ordnance Disposal, and MP. Infantry, Combat Engineers, and Explosive Ordnance Division are all male combat MOSs. It is estimated that fewer than 25% of the MP MOS participants will be women based on the gender composition of the Military Police who served in Iraq and Afghanistan. Although it is not anticipated that we will have sufficient numbers of women subjects to have adequate power to detect gender effects on study outcomes, gender will be used as stratification variable during randomization to ensure that women subjects have an equal chance of receiving active drug. Gender will be used as a covariate in the analysis and results may generate hypotheses for future gender-targeted studies of mTBI. Persons of all races and ethnic backgrounds will be eligible. The veteran patient population at VAPSHCS is comprised of 75% Caucasians, 14% African Americans, 4% Native Americans, 3% Hispanic Americans, 2% Asian Americans, and 2% "other". No differences based on racial/ethnic differences are expected. Ethnic and minority composition of participants in [name] ongoing VA Rehab R&D Merit Review: "Mild TBI and Biomarkers of Neurodegeneration" has been comparable to the overall Veteran population.

5. de Leon MJ, DeSanti S, Zinkowski R, et al. Longitudinal CSF and MRI biomarkers improve the diagnosis of mild cognitive impairment. *Neurobiol Aging*. 2006;27(3):394-401.

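### Age is a stratification factor in the randomisation section but missing from the ANCOVA that is meant to contain the stratification factors

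*Combined protocol and SAP*

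**What the plan says.** The document describes the stratification in three places.

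- *Study procedures, paragraph on randomisation and titration:* "Stratification factors will include age (<40 vs ≥ 40 years), gender, and number of blast trauma exposures (<5 and ≥5"). The same paragraph adds: "Separate blocked sequences will be generated for each of the three strata".
- *Data Analysis, Sample Size, Effect Size, and Power:* "we will stratify during randomization by two factors that potentially influence t-tau" levels, which it names as gender and number of blast exposures. Just before this it argues that the young age range should reduce variability, "since t-tau is correlated with age".
- *Statistical analysis, Primary analysis plan:* besides baseline value and treatment arm, the predictors are "the variables that were used for stratification of treatment assignment (i.e., gender and number of blast exposures"). The same list is given again for the cognitive scores.

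The section on inclusion of women and minorities says "Gender will be used as a covariate in the analysis", which fits the analysis plan but does not mention age. Age is a covariate in no model that the document describes.

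The label of the exposure variable also shifts. The analysis plan first lists the categorical variables as "Gender, APOE genotype, and number of mTBIs" (split at 5), and a few sentences later refers to blast exposures. The randomisation paragraph stratifies on blast exposures.

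**The concern.** The analysis plan sets a sensible rule, adjusting for whatever was stratified, and then closes the list without a factor that the randomisation section names. Two primary models can therefore be defended from the same text for four confirmatory endpoints: one follows the rule, the other follows the parenthesis. That choice should not be open once data are seen.

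If age really is stratified, leaving it out has a known effect. Stratification makes the arms similar in age, so the treatment estimate varies less than it would under simple randomisation. A model without age leaves the age variation in the residual, so its standard error is too large. The test is conservative, and the precision that the power section expects from stratifying is only partly collected.

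The randomisation paragraph also leaves open how many lists to prepare. Three two-level factors cross to 8 strata and two cross to 4. The stated number, three, is neither.

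**Working it through.** **1. The plan's own power figure.** Inputs from the power section: 50 per arm, α = 0.05/4 = 0.0125, effect sizes 0.68 and 0.77. The section does not state sidedness; two-sided is used here because it reproduces the figures.

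- Noncentrality: d × √(50/2) = 0.68 × 5 = 3.40 and 0.77 × 5 = 3.85.
- Critical t on 98 df at 0.0125 two-sided: 2.545.
- Power: 80.2% and 90.2%, against the stated 80% and 90%.

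The figures reproduce, and no stratification factor enters the calculation, so the conflict does not undermine them.

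**2. Number of strata.** With age: 2 × 2 × 2 = 8. Without age: 2 × 2 = 4.

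**3. Direction of the effect if age is stratified but omitted.** Let R² be the share of residual variance explained by the age stratum. With perfect balance the true standard error is √(1 − R²) times the one the model reports. The per-test size is then about 2 × [1 − Φ(2.498/√(1 − R²))], where 2.498 is the two-sided normal critical value at 0.0125.

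- R² = 0.04: 2.498/0.980 = 2.549, size 0.0108.
- R² = 0.10: 2.498/0.949 = 2.633, size 0.0085.

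The size falls below 0.0125. It does not rise.

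**4. Simulation.** The document gives no size for the age effect, so this part rests on assumptions: age explains 2%, 5% or 10% of residual variance after baseline adjustment; 8% women; half with five or more exposures; age either uniform on 21–50 or with 20% aged 40 or over. Design: 120 randomised in permuted blocks of 4 or 6 within 8 strata, 100 analysed, completers at random. ANCOVA contains baseline, gender and exposure stratum. There were 40,000 runs for size (simulation error about 0.0006) and 15,000 for power at d = 0.68 (about 0.3 points). Each cell shows uniform age / 20% aged 40 or over.

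| Age share | Size without age | Power without age, % | Power with age stratum, % | Power with continuous age, % |
|---|---|---|---|---|
| 2% | 0.0112 / 0.0119 | 79.6 / 79.0 | 79.9 / 79.4 | 80.0 / 79.7 |
| 5% | 0.0116 / 0.0117 | 80.1 / 79.5 | 81.7 / 80.7 | 81.8 / 81.5 |
| 10% | 0.0100 / 0.0108 | 80.1 / 79.2 | 82.5 / 81.3 | 83.9 / 83.4 |

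By subtraction, adding the age stratum gains 0.3–0.4, 1.2–1.6 and 2.1–2.4 points. Adding continuous age gains 0.4–0.7, 1.7–2.0 and 3.8–4.2 points. With the stratum in the model, size is 0.0116–0.0128.

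**5. A stronger age effect.** A second simulation put the whole effect on the under-40 / 40-and-over split, with 30% aged 40 or over. Size without age was 0.0108, 0.0091 and 0.0089 at shares of 4%, 10% and 16%; the power gains from adding the stratum were about 2, 4 and 6 points. At a share of zero the two models did not differ.

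**6. The other reading.** If only gender and blast exposures are stratified (4 strata, uniform age), size without age is 0.0123, 0.0131 and 0.0118 at 2%, 5% and 10%. That is nominal within simulation error, so the model then matches the design.

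**The case against.** The best case against acting is that little is at stake. Age as a stratifier appears in one paragraph only; the power section and both model statements leave it out. If those are right, the ANCOVA is correct and the error is a stray word in the randomisation paragraph. If they are wrong, the consequence is mild conservatism, its size rests on assumed age effects, and at a 2% share the gain is no larger than simulation error. The absolute power figures also treat 0.68 as a multiple of the ANCOVA residual SD. The plan illustrates its effect size with change from baseline; on that scale baseline adjustment would lift power, and the loss would matter less.

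All of this stands as a limit on size. None of it removes the conflict. One might read the power section as naming only the stratifiers thought to affect t-tau, but that section itself ties t-tau to age, and the analysis plan's list is closed. The stated number of strata may be loose wording for three factors. That reading supports the randomisation paragraph and so makes the missing covariate the error. The sentence on gender as a covariate is not a general rule about stratifiers, and no weight is placed on it.

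**Conclusion.** The concern holds. The document gives two incompatible accounts of the stratification, and under one of them the primary ANCOVA omits a stratification factor that it says it includes.

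The effect is small. If age is stratified and omitted, size is about 0.010–0.012 against 0.0125, and about 0.3 to 2.4 points of power are forgone relative to adding the age stratum, for assumed age shares of 2% to 10%. A stronger effect concentrated on the age split would cost more, and no age effect would cost nothing. The document states an age relation for t-tau only. Adjusting for baseline t-tau absorbs part of it, and nothing is said about p-tau, the ratio or BDNF. The treatment estimate is unbiased, omitting age does not inflate the false-positive rate, and the stated power stands.

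It should be fixed because the primary model ought to be unambiguous before unblinding and because the correction costs almost nothing.

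**What to change.** - Decide which factors are stratified and make the randomisation paragraph, the power section and the primary analysis plan agree.
- If age is one of them, add it to the biomarker and cognitive ANCOVAs. The under-40 / 40-and-over stratum is the minimum; continuous age is an acceptable alternative. Name the choice in advance. Preferably carry it into the secondary mixed model, for which no covariates are listed.
- Replace the count of strata with a statement that separate permuted-block lists are prepared for each crossed stratum: 8 with age, 4 without. When choosing, note that with an assumed 8% women (120 × 0.08 = 9.6 subjects) the four female strata of the eight-list design would hold about 9.6/4 = 2.4 subjects each, fewer than a block of four.
- Call the <5 / ≥5 covariate number of blast exposures throughout.

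The cost is a few words and one degree of freedom. Age is already collected on everyone, and no new data are needed.
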